[figure not shown]

Study title	REtinaL Imaging & Ambulatory BLOOD PrEssure: validating ultra-widefield retinal imaging derived biomarkers against ambulatory blood pressure (RELIABLE)
Co-sponsors	The University of Edinburgh and NHS Lothian
Study Protocol version Number and Date	Version 2.0 04th December 2018
Statistical analysis plan version Number and Date	Version 1.0. 14 th February 2020
ClinicalTrials.gov identifier	NCT04118205
Sponsor number	AC18080
IRAS project number	228069
Chief Investigators	Approved
[name] NHS Lothian [contact]	Signature and date
[name] NHS Lothian [contact]	Signature and date
Sponsor representative	
[name] Head of Research Governance, ACCORD NHS Lothian [contact]	Signature and date
Funder representative	
[name] [name] Optos plc [name]	Signature and date  Signed by: [name] Date: 14 Feb 2020 14:55:25 +00:00 Reason: Approved By DocuSign

Primary Objective

Arterial to venous ratio (AVR) measurements from the left eye (semi-automated and automated) will be investigated against clinic blood pressure (average of 4 measurements) for performance of classification of hypertensive status (based on gold standard; daytime mean ambulatory systolic blood pressure).

Dependent variable

Hypertensive status. Hypertension defined as daytime average ambulatory systolic and/or diastolic blood pressure (ABPM) measurement greater than or equal to 135/85 mmHg, respectively.

Independent variables

AVR; semi-automated and automated measurements in both right and left eyes. These measurements are obtained using computer code, please see appendix for details of the method. Also in the appendix are the secure hash algorithm (SHA) checksums of the code and results, which enables anyone to verify the code that is used is exactly the same as when the checksum was created.

Clinic blood pressure (CBP); average of four readings, two per arm.

Primary analysis

Demographics of the sample will be described. Descriptive statistics for quantitative parameters will be presented as mean, standard deviation (SD); or median and inter-quartile range (IQR) for skewed data.

Simple comparison analyses will be performed between those with and without hypertension, and those who are under treatment for hypertension vs those who are not, for each of the included variables. Univariate analyses will be completed using either a Pearson chi-square (for categorical variables) or independent samples t-test (for continuous variables). A p value of < 0.05 will be used to demonstrate a statistically significant difference.

Receiver operating characteristic (ROC) curves and area under the curve (AUC) estimates will be estimated for the prediction of hypertensive status.

In the primary analysis AVR measurements from the left eye (semi-automated and automated) will be investigated against clinic BP (average of 4 measurements) for performance of classification of hypertensive status (based on gold standard; daytime mean ABPM) measured by AUC. We have pre-specified hierarchical primary endpoints in the table below;

Exclusion criteria

The following data will be excluded from the analysis:

- Insufficient ABPM measurements; less than 70% successful daytime readings.
- Retinal image of inadequate quality for determination of AVR as defined in the appendix.

Step 1	Non-inferiority of semi-automated AVR measurements from the left eye (where unavailable, measurements from the right eye will be used) against CBP for predicting hypertensive status in the full sample where semi-automated AVR measurement is defined. If significant at $p < 0.05$ move on to Step 2
Step 2	Non-inferiority of automated AVR measurements from the left eye (where unavailable, measurements from the right eye will be used) against CBP for predicting hypertensive status in the full sample where automated AVR measurement is defined. If significant at $p < 0.05$ move on to Step 3
Step 3	Non-inferiority of semi-automated AVR measurements from the left eye (where unavailable, measurements from the right eye will be used) against CBP for predicting

	hypertensive status in the untreated sample where semi-automated AVR measurement is defined. If significant at $p < 0.05$ move on to Step 4
Step 4	Non-inferiority of automated AVR measurements from the left eye (where unavailable, measurements from the right eye will be used) against CBP for predicting hypertensive status in the untreated sample where automated AVR measurement is defined.

Hierarchical primary objectives each tested only if the preceding tests were significant.

Untreated patients are those who are not on any antihypertensive therapy at the time of ambulatory blood pressure monitoring.

The non-inferiority of retinal classification of hypertensive status compared with clinic blood pressure will be estimated using MedCalc and the R open source software based on one-sided Z-test. We will use a non-inferiority margin (Δ) on the AUC of 0.05. (This is the difference between the optimum method for combining multiple automated office blood pressure measurements, relative to ABPM, and a single blood pressure measurement [5].), P-values will be determined with a Wald-test.

The hierarchical analysis will negate the need to adjust p values.

Secondary analysis:

Right eye AVR for predicting hypertensive status.

Average of left and right eye AVR for predicting hypertensive status.

Regression analysis of AVR with ABPM as a continuous variable.

Using night-time mean ABPM as reference standard instead of daytime ABPM.

Using 24-hr mean ABPM as reference standard instead of daytime ABPM.

AVR and demographic info (age, sex, BMI, medication) for predicting hypertensive status.

Clinic BP and demographic info (age, sex, BMI, medication) for predicting hypertensive status.

Totally automated analysis (with automated instead of AB testing for image quality).

Tables

Table 1: Study sample and group comparison

Table 2: Logistic regression and ROC analysis results

Figures:

ROC curves for each of the models run

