Appendix

Assessment of artery vein ratio from scanning ophthalmoscope images.

During retinal imaging, most participants in RELIABLE had multiple images taken of the left eye and multiple images taken of the right eye. AB testing was used to select a single left and right eye for analysis. AB testing has been found to be an effective subjective method of ordering images in terms of quality. In the case of AB testing retinal images in RELIABLE, the original image was overlain with the vessel segmentation map so that both image and segmentation could be assessed. The AB testing was performed by an experienced researcher, where quality was assessed to maximise visible vasculature in measurement zone while minimising image artefacts such as eyelid and eyelash. This was performed as a pre-processing step before the automated and semi-automated artery vein ratio (AVR) analysis that is detailed below.

For each left and right eye pair per participant (where available), as identified by AB testing, the AVR was calculated. AVR was determined in an annular segment subtending 180° nasal to the optic disc and fixed on a line passing through the centre of the fovea and optic disc. It extended 6.5 to 8.5 optic disc radii from the optic disc centre.

Automated Method

AVR was evaluated in each ultra-widefield image as follows:

1. The optic disc location, and the fovea location were automatically detected [1]. These landmarks were used to establish the zone of measurement. A standard OD radius of 60 pixels was assumed.
2. Next, automatic segmentation of the retinal vessels was performed using a validated computer algorithm described elsewhere [2]. In brief, the green image was processed using scaled filters to increase vessel contrast with respect to the background. The filters exploited the morphology of the vessels as well as their cross-sectional intensity profile. A supervised machine learning classifier trained on a separate image set categorised image pixels as vessel or non-vessel, Figure 1 (d).
3. The calibre (in microns) for each vessel segment in the measurement zone was estimated as the average distance between parallel splines automatically fitted to the detected vessel edges [3]. Only vessel segments ≥ 26 pixels in length were measured. Segments below this length were discarded.

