- [5] Myles N Moore, Martin G Schultz, Mark R Nelson, J Andrew Black, Nathan B Dwyer, Ella Hoban, Matthew D Jose, Wojciech Kosmala, Monika Przewlocka-Kosmala, Jowita Zachwyc, Petr Otahal, Dean S Picone, Philip Roberts-Thomson, Panagiota Veloudi, James E Sharman, Identification of the Optimal Protocol for Automated Office Blood Pressure Measurement Among Patients With Treated Hypertension, *American Journal of Hypertension*, Volume 31, Issue 3, March 2018, Pages 299–304, <https://doi.org/10.1093/ajh/hpx180>

Checksums

Repository	Git commit checksum
Auto a (data files for outer measurement area)	7a0569f7d0866a6a7f0ff8d796e8292029609e68
Auto b (data files for inner measurement area)	875cda3a0c47207d11dcde93e8703911604a5f76
Semi a (data files for outer measurement area)	e8c08162c23d051e74b7c2c1193cb1d4c4432a06
Semi b (data files for inner measurement area)	c7628d80bc852c349d7e35b4f8c79eabd81da477
Ab testing: code for performing AB testing	458c9881691b76502e3e0ccddd90bb19986da765
Annotation (GUI for manual correction)	9b33115fad2c3b4ecc2342620ce4ec6607ca2d29
Auto (Auto analysis code)	2f291c84fc61aff7babe90ae1dbff27938d08f49
Avr (Semi automated analysis code)	37d281df2c925a75b545aab35ce79db5cbc2179b
Odfovea (manual OD and fovea annotation)	8134f48ada6d3bead4faf23846375eb753691117
Projection (Stereographic projection code)	983415ece2b38f1559817a35f4825d0774e46211
Scripts (code)	c8ac3f9a12ddd80e32f989eb6e5e53c58aff15d9
Sort (code)	868fd71cb355e4a480a172f360485f2629f32bdd
Results for stats (excel sheets with results for [name])	c3cf652e960f4dba5210c2f81bd892fd09dd9ccd
Odfovea auto (Automated OD and fovea detection)	2fec5fb0c2962695f5c8df11e1e9e9f89ab3e9da
Filename	SHA-256 Checksum
reliable_git_repo.zip (a zip folder containing the above git repos minus data files)	bb0c6f519e8a315039576a2fdc61525c3c94951f2628ec0a5d0d8e08c89f65fd
reliable_results_a.zip (a zip folder containing the outer area data files)	eaf7fca57db2e04a53b2d5e84d499a584ea57937ed293ab53a10cf04b2064f0e
reliable_results_b.zip (a zip folder containing the inner area data files)	ca4a4a3b4533a33cf01368b64dd7b4790cec505253aba5da394eede50d1f8eae

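### Should the primary AVR be the mean of both eyes instead of the left eye alone?

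*SAP*

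**What the plan says.** The Primary Objective names the left eye: "Arterial to venous ratio (AVR) measurements from the left eye (semi-automated and automated) will be investigated against clinic blood pressure". The Primary analysis section repeats this, saying that "AVR measurements from the left eye (semi-automated and automated) will be investigated against clinic BP (average of 4 measurements"), and the table of hierarchical steps adds the fallback. Step 1 reads "Non-inferiority of semi-automated AVR measurements from the left eye (where unavailable, measurements from the right eye will be used) against CBP", and Steps 2 to 4 use the same eye rule. Each participant therefore contributes one AVR value per method.

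Under Independent variables, AVR is listed as "AVR; semi-automated and automated measurements in both right and left eyes", and clinic blood pressure as "average of four readings, two per arm". The Appendix says "For each left and right eye pair per participant (where available), as identified by AB testing, the AVR was calculated". The Secondary analysis list includes right-eye AVR on its own and "Average of left and right eye AVR for predicting hypertensive status". The Checksums table at the end of the Appendix has an entry "Results for stats (excel sheets with results for" the statistics, together with archives of result files.

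The SAP gives no inter-eye correlation, eye-specific precision, expected AUC, sample size, prevalence or share of participants with two measurable eyes.

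**The concern.** The comparison looks uneven. Clinic blood pressure is averaged over four readings and both arms, while AVR comes from one eye although a second was usually to hand. Measurement noise in a marker pulls its AUC towards 0.5. In a non-inferiority test with a margin of 0.05 on the AUC, a loss of two or three hundredths is a large part of the margin. Step 1 also gates Steps 2 to 4, so noise that costs Step 1 would cost all four primary claims. The data for a two-eye mean already exist, so the remedy appears to cost only a change of wording.

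**Working it through.** The SAP states no power or AUC figure, so there is nothing of its own to reproduce. Taken from the SAP: margin 0.05, one-sided Z-test, p < 0.05 at each step. Everything else below is an assumption.

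**1. Gain when the two eyes are equally informative.** In an equal-variance binormal model with single-eye SD 1, AUC = Φ(d/√2). With within-group inter-eye correlation r, the mean of two eyes has variance v = (1+r)/2, so AUC(mean) = Φ(z(AUC)/√v). For a single-eye AUC of 0.75, z = 0.6745:

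| r | v | AUC of mean | Gain |
|---|---|---|---|
| 0.5 | 0.75 | 0.782 | 0.032 |
| 0.7 | 0.85 | 0.768 | 0.018 |
| 0.9 | 0.95 | 0.756 | 0.006 |

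**2. Some participants have one eye only.** With share b bilateral, independent of hypertension, AUC = b²Φ(d/√(2v)) + 2b(1−b)Φ(d/√(1+v)) + (1−b)²Φ(d/√2). At b = 0.8 the gains from 0.75 are 0.025, 0.014 and 0.004. At b = 0.6 they are 0.018, 0.010 and 0.003.

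**3. Step 1 power.** Power = Φ((AUC_AVR − AUC_CBP + 0.05)/SE − 1.645), with Hanley-McNeil standard errors, 150 hypertensive and 150 not, and correlation 0.2 between the two AUC estimates. With both AUCs at 0.75, each has a standard error of 0.0281, so SE = 0.0281 × √(2 × 0.8) = 0.0355. Single-eye power is Φ(0.05/0.0355 − 1.645) = Φ(−0.24) = 41%. With 80% bilateral:

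| Clinic BP AUC | Single-eye AVR AUC | Single-eye power | Two-eye power at r = 0.5 / 0.7 / 0.9 |
|---|---|---|---|
| 0.75 | 0.75 | 41% | 70 / 57 / 46% |
| 0.75 | 0.72 | 14% | 33 / 23 / 16% |
| 0.80 | 0.75 | 5% | 19 / 11 / 6% |
| 0.75 | 0.65 | 0.15% | 0.6 / 0.3 / 0.2% |
| 0.80 | 0.70 | 0.1% | 0.7 / 0.3 / 0.2% |

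The gain matters only when AVR nearly matches clinic blood pressure and the eyes are not highly correlated.

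**4. When the right eye is noisier.** If its SD is k times that of the left with the same mean shift, v = (1+k²+2rk)/4. Averaging breaks even at k = √(r²+3) − r, which is 1.30, 1.17 and 1.05 at r = 0.5, 0.7 and 0.9. With k = 1.1 and 80% bilateral (one-eye participants kept at SD 1), the 41% in the first row becomes 60%, 47% and 36%: a loss at r = 0.9.

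**5. When the right eye separates the groups less well.** If its mean shift is s times that of the left with equal SDs and all participants bilateral, AUC(mean) = Φ(z(AUC) × ((1+s)/2)/√((1+r)/2)). With s = 0.8 and a left-eye AUC of 0.75 the results are 0.758, 0.745 and 0.733: a loss at r = 0.7 and at r = 0.9.

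**6. Is the rule itself sound?** The primary-analysis sentence and Steps 1 to 4 agree on the left eye; the fallback in the steps settles what happens when it is missing. Nothing contradicts this elsewhere, and the choice of eye does not affect the validity of the test.

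**The case for a change.** The strongest case for changing the plan is that AVR has visible single-eye noise. By the Appendix it rests on at most three arteries and three veins, in one image per eye chosen subjectively. The SAP gives no reason for preferring the left eye, and it derives its own margin from the difference between combining several office readings and taking one, so it accepts that replication matters for blood pressure. Averaging would need no new data and lose no participant, and a secondary result cannot rescue a failed Step 1.

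The arithmetic behind this stands: with equally informative, moderately correlated eyes, the mean is the better marker. The conclusion does not follow. AVR is not a single raw reading, since it already averages several vessels from an image selected for quality. The SAP supports neither equal precision nor equal separation in the two eyes, and modest departures cancel or reverse the gain. The change would also turn the index test from one eye into a mixture of one-eye and two-eye values. Finally, the Appendix describes the AVR measurements as done and lists checksummed result files. Redefining the primary marker now would be defensible only if AVR had not yet been linked to ambulatory pressure, which the SAP does not state; if it had been linked, the primary should stay as it is.

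**Conclusion.** The concern does not hold. The left-eye rule is a clear, prespecified and valid way to obtain one value per participant, and the two-eye mean will be reported as a secondary analysis. Promoting it could raise Step 1 power noticeably (41% to 57% at r = 0.7 with 80% bilateral). That requires AVR to be about as good as clinic blood pressure and the eyes to be similarly precise and informative. It would make no practical difference if AVR is about 0.10 lower, and could do harm if the right eye is somewhat worse. All these figures depend on assumed correlations, AUCs, sample size and bilateral share. Which eye rule to make primary is a judgement on which reasonable statisticians may differ, and the plan has made it openly. No change is needed.

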4. A deep learning model was used to perform classification of vessel segments as artery or vein (Optos; proprietary). In brief, centreline pixels from each vessel segment were extracted and patches of 129 x 129 pixels from contrast enhanced red green pseudo-colour images were passed to a CNN model. The output from the CNN model was a probability of each vessel segment centreline pixel being artery. The average probability of centreline pixels was found, and the vessel segment was classed as artery if the average probability was ≥ 0.5 , otherwise it was classed as vein.
5. Finally, AVR was calculated as the ratio of the average calibre of the 3 widest arteries and the average of the 3 widest veins. Fewer artery and vein segments were used when less than 3 were available. Only vessel segments whose calibre was determined to be ≥ 0.06 mm and ≤ 0.25 mm were used for AVR calculation.

Semi-Automated Method

Note: please see [4] for recently published results of the semi-automated method.

AVR was evaluated in each ultra-widefield image as follows:

1. The optic disc location, its approximate outline, and the fovea location were manually annotated by a trained operator. These landmarks were used to establish the zone of measurement, Figure 1 (a).
2. Next, automatic segmentation of the retinal vessels was performed using a validated computer algorithm described elsewhere [2]. In brief, the green image was processed using scaled filters to increase vessel contrast with respect to the background. The filters exploited the morphology of the vessels as well as their cross-sectional intensity profile. A supervised machine learning classifier trained on a separate image set categorised image pixels as vessel or non-vessel, Figure 1 (d).
3. The calibre (in microns) for each vessel segment in the measurement zone was estimated as the average distance between parallel splines automatically fitted to the detected vessel edges [3]. Only vessel segments ≥ 26 pixels in length were measured. Segments below this length were discarded.

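### Does the missing image-quality cut-off leave open which eye's AVR enters Steps 2 and 4?

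*SAP*

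**What the plan says.** Under Exclusion criteria the SAP introduces its list with "The following data will be excluded from the analysis". The second item is a "Retinal image of inadequate quality for determination of AVR as defined in the appendix".

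Each of the four hierarchical steps takes the left-eye artery-to-vein ratio (AVR), and "where unavailable, measurements from the right eye will be used". The analysis set follows the method: Step 2, for example, is run "in the full sample where automated AVR measurement is defined". Step 4 is the same in untreated participants.

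The Appendix describes how one image per eye was chosen. It says "most participants in RELIABLE had multiple images taken of the left eye", and likewise of the right, and that "AB testing has been found to be an effective subjective method of ordering images in terms of quality". This selection came before both the automated and the semi-automated measurement. Both methods then measure only segments of at least 26 pixels, keep calibres from 0.06 to 0.25 mm, and form the ratio: "AVR was calculated as the ratio of the average calibre of the 3 widest arteries and the average of the 3 widest veins". Fewer segments are used when three are not available. Only the semi-automated method has an operator mark false vessels and correct artery and vein labels.

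The Secondary analysis list includes a "Totally automated analysis (with automated instead of AB testing for image quality").

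**The concern.** The exclusion seems to point to a definition that is not there. Ranking images picks the best one for an eye but does not say when the best is still too poor, and a participant with a single image has nothing to rank. The length and calibre limits act on vessel segments, not on images.

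Two readings then seem possible.

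- **Image-level:** an image judged inadequate is rejected even if the software returns a ratio from it, and the right eye takes its place.
- **Computability:** an image is inadequate only when no ratio can be formed from it.

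They could part company in Steps 2 and 4, where no operator removes eyelashes or choroidal vessels. A poor left image may still return an automated AVR; it stays in on the second reading and is replaced on the first. Because the participant stays in either way, the clinic blood pressure AUC does not change. Any change in the AVR AUC passes in full into the difference tested against the 0.05 margin.

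A smaller point is that the automated quality step in the secondary analysis is not described in the Appendix.

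**Working it through.** **1. The texts side by side.**

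- The exclusion's closing words about the appendix can attach to the image quality or to the determination of AVR. The Appendix has no definition of the first. It does define the second: measurement zone, segment length, calibre range, and the mean of up to three widest arteries over that of up to three widest veins.
- A ratio needs at least one qualifying artery and one qualifying vein. With none of either, no AVR exists. The method as written thus supplies its own objective floor.
- The steps restrict the sample to participants whose AVR is defined for the method concerned. This matches the computability reading.
- The unit of exclusion also follows. An image that yields no AVR makes that eye unavailable, the other eye is used, and a participant with neither falls outside the step's sample.
- The image-level reading cannot be carried out from the document, since an analyst would have to invent a threshold.

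**2. What is already fixed.** The Appendix reports image selection and measurement in the past tense. The Checksums list covers the analysis code, the data files and the result sheets prepared for the statistics. The text does not say whether those files already omit any image on quality grounds. For the results to diverge, however, someone would have to reject images after that point.

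**3. Possible size.** The SAP states no sample size, expected AUC or share of poor images, so there is no figure of its own to reproduce. Apart from the margin of 0.05 and the one-sided 0.05 test, every input below is an assumption.

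Let A be the AUC of a good AVR. Let g be the share of participants whose left image would be rejected on the image-level reading but carries a wholly uninformative automated AVR on the other. Suppose the right eye is as good as the left.

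- Image-level reading: AUC = A
- Computability reading: AUC = A(1 − g) + 0.5g
- Shift in the AVR-minus-clinic difference = −g(A − 0.5), at any prevalence

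| g | A = 0.65 | A = 0.75 | A = 0.85 |
|---|---|---|---|
| 1% | 0.0015 | 0.0025 | 0.0035 |
| 2% | 0.0030 | 0.0050 | 0.0070 |
| 5% | 0.0075 | 0.0125 | 0.0175 |
| 10% | 0.0150 | 0.0250 | 0.0350 |

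At A = 0.75 these shifts are 5%, 10%, 25% and 50% of the margin (for example 0.0125 / 0.05 = 0.25). A simulation with 400,000 participants agreed with the formula to within 0.001.

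**4. Effect on the verdict of Step 2.** The simulation assumed N = 200, 50% prevalence, both AUCs 0.75, within-group correlation 0.2 and a paired DeLong standard error.

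- Taken alone, Step 2 passes in 0.304 of runs on the image-level reading and 0.211 on the computability reading at g = 5%. The verdict differs in 10.9% of runs. At g = 2% the figures are 0.314, 0.275 and 5.5%.
- Step 2 is reached only if Step 1 succeeds. A separate run without that condition gave differing verdicts in 11.4% (g = 5%) and 6.0% (g = 2%). Counting only runs in which Step 1 passed gave 7.3% and 3.9%. This assumes a semi-automated AUC of 0.75 and a within-group correlation of about 0.94 between the two methods.
- If, in addition, half the affected AVRs keep their signal and 30% of substituted right eyes are themselves affected, the figures fall to 4.3% and 2.4%.
- The shift at g = 5% is 0.0125 against a mean standard error of 0.044, or 0.0125 / 0.044 = 0.28 of a standard error.

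**The case for a change.** The best case for a change is that the exclusion adds nothing if it only repeats what a defined AVR already requires, so its authors may have meant a separate judgement of the image. The checksums do not settle this, because the text does not say that the result files carry a quality flag or already apply the left/right rule, and the exclusion is worded in the future tense. The rule bears on primary endpoints, and one sentence would remove the doubt.

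Part of this stands. No image-level criterion is given, and a sentence would make the text tidier. But an exclusion that overlaps the step definitions is redundant, not contradictory. The sentence one would add states the reading that the steps already favour, so it would not alter the analysis.

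Two further points carry little weight. Steps 1 and 2 may use different eyes of the same person, but this follows from method-specific availability, which the plan states openly. The undescribed automated quality step belongs to one secondary analysis outside the hierarchy and cannot affect Steps 2 or 4. The repository labels do not settle whether its code is held, since two of them (Scripts and Sort) do not say what they contain.

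**Conclusion.** No change to the plan is called for. The Appendix does lack a pass/fail criterion for images, but the reading that can be executed, and that fits the wording of the steps, is that an eye has no AVR when the method cannot form one. An analyst working from this text with the checksummed code and results would arrive there without inventing anything, and nothing shows that the result would be wrong or biased.

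The size of any effect cannot be established from the document. On the assumptions above it is small at 1–2% of left images (0.0025 to 0.005 in AUC at A = 0.75) and would matter more at 10% (0.025). Choosing the best image per eye, with the vessel map overlaid and eyelid and eyelash artefacts kept to a minimum, makes low shares plausible but does not guarantee them. The figures also lean upward, because they treat an affected AVR as pure noise although it averages up to three vessels of each type, and treat the substituted eye as always sound. The conclusion would change only if images were rejected on quality by an unstated rule outside the locked results; the SAP gives no sign of that.

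### Does limiting Steps 1 to 4 to participants with a defined AVR leave the non-inferiority comparison with clinic blood pressure unsound?

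*SAP*

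**What the plan says.** The SAP's Primary analysis sets out four hierarchical non-inferiority steps, each comparing AVR with clinic blood pressure (CBP) by AUC. Step 1 takes semi-automated AVR "against CBP for predicting hypertensive status in the full sample where semi-automated AVR measurement is defined". Step 2 takes automated AVR "against CBP for predicting hypertensive status in the full sample where automated AVR measurement is defined". Steps 3 and 4 repeat the pair in untreated participants, with the matching restriction. The left eye is used, but "where unavailable, measurements from the right eye will be used", so a participant is lost only when neither eye yields a value. The Exclusion criteria name the same loss separately: "Retinal image of inadequate quality for determination of AVR as defined in the appendix". The margin is "on the AUC of 0.05", tested one-sided.

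The Appendix describes two routes to AVR. Under the Automated Method, "The optic disc location, and the fovea location were automatically detected". Under the Semi-Automated Method, "The optic disc location, its approximate outline, and the fovea location were manually annotated by a trained operator", and the operator then marks false vessels and corrects artery/vein labels. The Secondary analysis section lists eight analyses. None is stated to include participants without an AVR. The Tables section gives two table titles and no contents.

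**The concern.** When a new test is compared with an established one, setting aside the new test's failures can favour it. Clinic pressure needs no image, so someone who cannot be imaged still has a clinic reading. That reading is dropped only because AVR failed. In a non-inferiority setting such selection could help the test pass, and poor image quality might be related to hypertensive status.

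The set also depends on the method. Manual landmarks and operator correction could rescue or remove participants differently from the automated route. The CBP AUC in Step 1 could then rest on slightly different people from that in Step 2, and likewise for Steps 3 and 4.

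If many participants had no AVR, a claim of non-inferiority in the measurable group could be read as a claim about everyone who attends for imaging.

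**Working it through.** **Is anything in the SAP contradicted?** Set side by side, the wording of each step, the right-eye fallback and the exclusion of inadequate images all point the same way: the comparison is made where AVR exists. No other part of the SAP claims a result for all participants regardless of AVR.

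**Is each comparison internally sound?** Within a step, AVR and CBP are evaluated in the same participants against the same ambulatory reference. Losing a participant removes both tests together, so the AUC difference is a valid paired contrast for the stated set. Differing sets between Steps 1 and 2 would matter if the plan compared the two AVR methods with each other. It does not; each step compares one method with CBP in that method's own set.

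**How different can the sets be?** Both methods start from the same selected images and share the vessel segmentation, the 26-pixel minimum length, the artery/vein model, the 0.06 to 0.25 mm calibre limits and the allowance for fewer than three vessels. They differ in landmarks and in operator correction. Most participants had several images per eye. The SAP gives no count, so the difference cannot be sized from it.

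**Can the effect of the excluded participants be sized?** The SAP states no failure rate, expected AUC or sample size, so there is no figure of its own to reproduce. Assume a share f without AVR, equal in both classes, an AVR AUC of A = 0.75 in the rest, and a CBP AUC that does not change when the excluded people are added. The loss in AVR's AUC depends on the score given to a missing AVR:

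- One midpoint score (binormal model, d = √2 × Φ⁻¹(A) = 0.954): AUC = (1−f)²A + 2f(1−f)Φ(d/2) + 0.5f², with Φ(d/2) = 0.683.
- Random draw from the pooled observed AVRs: loss = f(A − 0.5).
- Every affected pair counted as a tie: loss = [1 − (1−f)²](A − 0.5).
- Worst case, every affected pair counted against AVR: loss = A[1 − (1−f)²].

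| f | Midpoint | Random draw | Tie | Worst case |
|---|---|---|---|---|
| 5% | 0.0070 | 0.0125 | 0.0244 | 0.0731 |
| 10% | 0.0145 | 0.0250 | 0.0475 | 0.1425 |
| 20% | 0.0313 | 0.0500 | 0.0900 | 0.2700 |

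For example, at f = 10% the tie rule gives (1 − 0.81) × 0.25 = 0.0475 and the random draw gives 0.10 × 0.25 = 0.025. The worst case reaches 0.05 at f = 1 − √(1 − 0.05/0.75) = 3.4%.

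If failure is related to status, the rule still dominates. Scoring all failures as test-negative at A = 0.75 costs 0.061 when failure is 10% in hypertensives and 5% in others, but 0.011 when those rates are swapped.

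**Would a test decision move?** With the random draw, f = 5%, both AUCs 0.75, prevalence 50% and within-class correlation 0.2 (all assumed), simulated standard errors of the AUC difference are 0.0648, 0.0457 and 0.0321 for n = 100, 200 and 400. The shift in Z is 0.0125 divided by each: 0.19, 0.27 and 0.39. Under those assumptions only a result close to the threshold would change.

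**The case for a change.** The best argument on the other side is practical. A reader deciding whether retinal imaging could stand in for a clinic reading needs to know how often imaging fails, under each method, and whether the conclusion survives when failures are counted. The SAP lists neither the count nor such an analysis. AVR values are already computed and their files checksummed, so a count would cost almost nothing, and a supportive analysis would leave the hierarchy and the significance level untouched.

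Much of this is fair as advice. The description of the analysis sets is accurate, and the count would be informative. It does not show a fault in the plan. Table 1 is described only as covering the study sample and group comparison, so a count not named there is no evidence that it will go unreported. The protocol, which is not at hand, may also deal with unusable images. The supportive analysis would need a scoring rule, and a failed image gives no test result at all. A random AVR drawn without regard to status weakens the AUC by construction, so whether non-inferiority then holds partly reflects the rule. Added as description with no test decision, as would be needed to leave the hierarchy alone, it could not alter the primary result.

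**Conclusion.** The concern does not hold. The SAP states its analysis set in all four steps, repeats it in the exclusion list, and compares the two tests in the same people within each step. Nothing is stated wrongly, contradicted or badly fixed. The primary result should be read as applying where AVR can be measured, which is what the steps say.

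The size of any effect from the excluded participants cannot be established from the SAP. At an assumed AUC of 0.75 with 10% lacking AVR, it runs from 0.015 to 0.048 under the three neutral scoring rules, below the 0.05 margin. With more failures, failure related to status, or a worst-case rule, it can exceed the margin. The spread comes from assumed failure rates, an assumed AUC, an assumed unchanged CBP AUC and the choice of rule, so it is no evidence for or against the plan. The right-eye fallback, repeat images and use of fewer than three vessels all work to keep failures few. What is left is a preference for additional reporting.
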